## 7.2 Measures to Adjust for Multiplicity, Confounders, Heterogeneity

We have two primary outcomes and so have adjusted the alpha for each primary outcome to 0.025 to give an overall alpha of 0.05 across both outcomes. We have several secondary outcomes. All secondary outcomes are exploratory and not powered for. We will therefore not adjust for multiple secondary outcomes but instead report all effect sizes, confidence intervals, and p values in order to let readers use their own judgment about the relative weight of the conclusions. This approach aligns with the usage of p-values favoured by the American Statistical Association [3].

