# 1 Introduction

Objectives	
1 Primary Objective
 
To compare the effects of knee OA educational information, with and without pathoanatomical content, on i) beliefs about the necessity to have an x-ray to confirm an OA diagnosis, and ii) beliefs about the necessity of joint replacement surgery in adults who have not had a knee joint replacement.
 
2 Secondary Objectives
 
To compare the effects of knee OA educational information, with and without pathoanatomical content, on management beliefs (about exercise and physical activity, the safety of exercise, medications, x-rays to determine treatment), level of concern, and OA knowledge in adults who have not had a knee joint replacement.
 
To explore whether a history of knee pain in the last 3 months moderates the effect of knee OA educational information without pathoanatomical content on the two primary outcomes, i) beliefs about the necessity to have an x-ray to confirm an OA diagnosis, and ii) beliefs about the necessity of joint replacement surgery in adults who have not had a knee joint replacement.

Study Design	Two-arm, parallel groups superiority randomised controlled trial.
Planned Sample Size	556 participants.
Study Procedures	
The entire trial will be administered in one single online survey. Participants will initially complete screening questions within the survey to determine eligibility. Eligible participants will then complete baseline outcome measures before being randomly allocated to one of two groups, both of whom will then be asked to immediately read a digital information pamphlet about knee OA on screen:
 
i) Control group: the pamphlet will contain information about OA including biological pathoanatomical information and language about OA
 
ii) Experimental group: the same pamphlet as the Control group, but with all pathoanatomical information and language relating to the structure of an OA joint removed.

	
All participants will complete outcome measures again, immediately after reading their allocated digital information pamphlet.

Duration of the study
	
Anticipated participant recruitment start: June 2022  Anticipated data collection end: June 2022
 
Based on our previous similar study [1], which recruited 735 participants in four days through a similar mechanism, we anticipate recruitment for this RCT will take approximately 6 days.

Figure 1. Study chart

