## 3 Analysis Objectives

The aim of this study is to compare the effects of knee OA educational information, with and without pathoanatomical content, on consumer OA management beliefs in adults who have not had a knee joint replacement.

### 3.1 Aim 1

To compare the effects of knee OA educational information, with and without pathoanatomical content, on i) beliefs about the necessity to have an x-ray to confirm an OA diagnosis, and ii) beliefs about the necessity of joint replacement surgery in adults who have not had a knee joint replacement.

We hypothesise that removing pathoanatomical content will lead to lower beliefs that an x-ray is necessary to confirm an OA diagnosis and lower beliefs that joint replacement surgery is necessary, compared to information with pathoanatomical content.

### 3.2 Aim 2

To compare the effects of knee OA educational information, with and without pathoanatomical content, on management beliefs (about exercise and physical activity, the safety of exercise, medications, x-rays to determine treatment), level of concern, and OA knowledge in adults who have not had a knee joint replacement.

We secondarily hypothesise that removing pathoanatomical content will lead to higher beliefs that exercise and physical activity is necessary and is safe, lower beliefs that medication is necessary, lower beliefs that x-rays are required to determine treatment, lower levels of concern, and higher OA knowledge.

To explore whether a history of knee pain in the last 3 months moderates the effect of knee OA educational information without pathoanatomical content on the two primary outcomes, i) beliefs about the necessity to have an x-ray to confirm an OA diagnosis, and ii) beliefs about the necessity of joint replacement surgery in adults who have not had a knee joint replacement.

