## 7 Statistical Methodology

### 7.1 Statistical Procedures

A biostatistician ([name], supervised by [name]) will analyse de-identified data in Stata version 16.1 (StataCorp LLC, College Station, TX, USA), while blind to group name. Descriptive data will be presented by intervention group as mean (SD), median (IQR) or n (%) as appropriate. Comparative analyses between groups will be performed using intention-to-treat according to the group to which the participant was randomised, irrespective of whether they adhered to the intervention by reading the information. The number included in each analysis will be reported. Standard diagnostic plots will be used to check model assumptions, including assessing linearity and homoscedasticity, where appropriate.

#### 7.1.1 Aim 1

Separate linear regression models for each primary outcome will be used to estimate the between-group mean (95% confidence interval, CI) difference in post-intervention scores, adjusted for the outcome at baseline. Post-intervention time point was 'immediately following reading a digital information pamphlet about knee OA on screen'.

#### 7.1.2 Aim 2

Separate linear regression models for each continuous secondary outcome will be used to estimate the between-group mean (95% CI) difference in post-intervention scores, adjusted for the outcome at baseline. For the ordinal secondary outcome, level of concern, ordinal logistic regression models will be fitted similarly, adjusted for the outcome at baseline. The proportional odds assumption will be assessed using the Brant test. If proportional odds cannot be assumed, multinomial regression models will be fitted. Results will be reported as odds ratios, or relative risk ratios if multinomial regression is used, with corresponding 95% CIs.

The mean (95% CI) effect on each of the primary outcomes, i) beliefs about x-rays and ii) beliefs about joint replacement surgery, of potential moderators, i) a history of knee pain in the past 3 months, ii) highest education level (as a binary variable, no tertiary versus some tertiary) and iii) ever sought care for knee pain from any healthcare provider for each group will be estimated using separate linear regression models for each outcome and each moderator, with an interaction term fitted between group and the potential moderator, adjusting for baseline scores of the relevant primary outcome.

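### The fixed 0.025/0.025 split is valid, but Holm's procedure keeps the same overall 0.05, is never less powerful, and costs little to adopt

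*SAP*

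**What the plan says.** SAP section 7.2 opens with "We have two primary outcomes" and sets the rule: the authors have "adjusted the alpha for each primary outcome to 0.025 to give an overall alpha of 0.05 across both outcomes". The threshold for one outcome does not depend on the result for the other, and the SAP contains no step-down or alpha-recycling rule.

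The primary hypothesis in section 3.1 expects an effect on both outcomes: "lower beliefs that an x-ray is necessary to confirm an OA diagnosis and lower beliefs that joint replacement surgery is necessary".

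Section 7.1.1 uses one baseline-adjusted linear model per outcome to "estimate the between-group mean (95% confidence interval, CI) difference in post-intervention scores". The Table 2 shell in Appendix 3 likewise shows a 95% CI and a p-value for each primary outcome.

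Section 1 gives a sample size of "556 participants". The SAP gives no power, effect size, SD or correlation behind it. Section 7.2 says only of the secondary outcomes "All secondary outcomes are exploratory and not powered for".

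**The concern.** The two rules differ in one situation. Suppose one primary outcome has p at or below 0.025 and the other has p between 0.025 and 0.05. Under section 7.2 the second outcome misses its threshold. Under Holm it is significant, and the overall error rate is still at most 0.05. The error rate that the plan sets for itself therefore does not require the stricter result.

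This matters most when both effects are real and neither is so large that both tests succeed anyway. The first condition is what the trial hypothesises. The power at stake is for each outcome and for both together. The chance of at least one positive primary outcome is not affected.

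**Working it through.** **Inputs from the SAP.** Two primary outcomes, 0.025 each, 0.05 overall (7.2); effects expected on both (3.1); 95% CIs (7.1.1 and Table 2).

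**Assumptions, not in the SAP.** Two-sided tests; approximately normal test statistics; power of 80% or 90% per outcome at 0.025; correlation between the two test statistics of 0 to 0.8.

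**1. The plan's own figure.** 0.025 + 0.025 = 0.05, as stated. For independent tests the exact value is 1 − 0.975² = 0.0494. The split is valid under any correlation.

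**2. Holm controls the same error.** If both null hypotheses are true, a false rejection needs at least one p ≤ 0.025, with probability at most 0.025 + 0.025 = 0.05. If only one is true, a false rejection needs that p ≤ 0.05, again with probability at most 0.05. In simulation under the joint null, the overall error is identical for the two rules: 0.0495 at correlation 0 and 0.0402 at 0.8.

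**3. Independent tests, by formula.** The two-sided critical values are 2.2414 (0.025) and 1.9600 (0.05).

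With 80% power at 0.025:
- Expected z = 2.2414 + 0.8416 = 3.0830, so power at 0.05 is Φ(3.0830 − 1.9600) = 0.8693.
- The chance that p falls between 0.025 and 0.05 is 0.8693 − 0.80 = 0.0693.
- Per outcome under Holm: 0.80 + 0.0693 × 0.80 = 0.855.
- Both, fixed split: 0.80² = 0.640.
- Both, Holm: 0.8693² − 0.0693² = 0.751. The subtracted term is the case in which neither p reaches 0.025.

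With 90% power at 0.025:
- Power at 0.05 is 0.9410.
- Per outcome under Holm: 0.90 + 0.0410 × 0.90 = 0.937.
- Both: 0.90² = 0.810 under the split, and 0.9410² − 0.0410² = 0.884 under Holm.

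**4. Correlated tests, by simulation** (2,000,000 draws per row; all entries in %):

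| Power each at 0.025 | Correlation | Per outcome, Holm | Both, split | Both, Holm | At least one, either rule |
|---|---|---|---|---|---|
| 80 | 0 | 85.5 | 64.0 | 75.1 | 96.0 |
| 80 | 0.5 | 84.6 | 68.7 | 77.8 | 91.3 |
| 80 | 0.8 | 83.8 | 72.9 | 80.4 | 87.1 |
| 90 | 0 | 93.7 | 81.1 | 88.4 | 99.0 |
| 90 | 0.5 | 93.0 | 83.2 | 89.3 | 96.8 |
| 90 | 0.8 | 92.5 | 85.7 | 90.6 | 94.4 |

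The rows at correlation 0 agree with step 3 within simulation error.

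**5. Only one real effect** (80% power, correlation 0). Power for the real effect becomes 0.80 + 0.0693 × 0.025 = 0.802, a gain of 0.2 points; in simulation it is smaller still at higher correlation. The false-positive rate on the outcome with no effect rises from 0.025 to 0.025 + 0.025 × 0.80 = 0.045, still within 0.05.

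**6. Tests against 95% CIs.** Under the current plan, a primary outcome with p between 0.025 and 0.05 has a 95% CI that excludes zero but is not significant. Under Holm this mismatch remains only when the other outcome has not reached 0.025.

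**The case against.** The strongest objection is that nothing in section 7.2 is wrong. The split is pre-specified, unambiguous and exact, and a trial sized at 0.025 per outcome keeps whatever power it was planned to have. This stands, and it is why the point is an efficiency suggestion only.

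Second, the size of the gain rests on a power that the SAP does not give and that may be in the protocol. This also stands. The gain in power for both outcomes falls from 11 points (80%, correlation 0) to about 5 points (90%, correlation 0.8), and shrinks further if both effects are large.

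Third, a fixed split allows simple simultaneous 97.5% CIs that match the tests, and Holm does not. That is a legitimate reason to prefer the split in general. It carries little weight here, because this plan reports 95% CIs and does not use that advantage. Showing a 97.5% and a conditional 95% interval for the same outcome would be awkward, so the fix below does not ask for it.

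A reader might infer that the plan gives up power on both primary outcomes in every case, or that a second outcome with p = 0.03 would be reported as a failure. The documents support neither. Power for at least one outcome is identical under the two rules, and Holm can add a rejection on one outcome only after the other has passed 0.025. The SAP uses no language of failure, and Table 2 would show the estimate, CI and p-value in any case.

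**Conclusion.** This is a cheap improvement, not an error or a contradiction. At the same overall 0.05, Holm is never less powerful than the split in section 7.2, and it is more powerful per outcome and for both when both effects are real, as section 3.1 hypothesises.

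Under the stated assumptions the gain is about 4 to 6 points per outcome and 7.5 to 11 points for both at 80% power each, and about 2 to 4 points per outcome and 5 to 7 points for both at 90%. It is zero for at least one outcome and negligible for a single real effect. The ordering of the two rules needs none of these assumptions; only the sizes do. The SAP does not support a claim that the trial is underpowered or that "556 participants" is the wrong number.

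**What to change.** In section 7.2, replace the alpha sentence with wording such as: *The two primary p-values will be tested by Holm's procedure at an overall two-sided alpha of 0.05. The smaller is compared with 0.025; if it is significant, the larger is compared with 0.05. If the smaller is not significant, neither outcome is declared significant.*

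In section 7.1.1 and the footnotes to Table 2, add that the 95% CIs for the primary outcomes are not adjusted for multiplicity and that significance is judged by the Holm rule on the p-values.

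The change must be made before any comparison between groups is seen. Keeping the analyst blind to group names, as section 7.1 provides, is not enough, because a two-sided p-value does not depend on the labels.

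The cost is one sentence and two short notes. The sample size is unaffected, because the first step is still at 0.025 and every rejection under the split is kept. The downside is that Holm has no simple matching simultaneous CIs, so intervals and tests may not always agree. The current pairing of 0.025 tests with 95% CIs already has this feature. If the sponsor prefers the fixed split, one sentence giving the reason would be enough.

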## 8 Sensitivity Analyses

If multiple imputation is used for the primary outcomes, sensitivity analyses will be conducted on complete case analysis.

## 9 QC Plans

Data quality will be checked/promoted through a process of identifying extreme values and checking the source of these values in case of a data entry error. A record of any/all manual corrections to data will be maintained. Calculations of scores from multi-item scales will be carried out using Microsoft Excel functions and cross-checked using other statistical packages to reduce errors.

## 10 Programming Plans

A list of all tables, figures, listings and their templates can be found in Appendix 3.

## VARIABLES IN THE DATA SET

Baseline descriptive measures		
Age	How many years old are you?	Years.
Gender	Are you...	1, Male 2, Female 3, Transgender male 4, Transgender female 5, Gender variant/non-conforming 6, Prefer not to say
Ethnicity	With what ethnicity do you most identify?	1, Australian/New Zealand 2, Aboriginal and Torres Strait Islander 3, European 4, Asian 5, Other Oceania 6, North African & Middle Eastern 7, Sub-Saharan Africa 8, North American 9, South American 10, Other (please specify)
State	What state do you live in?	1, ACT 2, NSW 3, NT 4, QLD 5, SA 6, TAS 7, VIC 8, WA
Height	What is your height?	Self-reported in metres
Weight	What is your weight?	Self-reported in kilograms
Education	What is the highest level of education you have completed?	1, Primary school 2, High school 3, Trade or trade certificate 4, University or tertiary institute degree 5, Higher university degree (e.g. Masters, PhD) 6, Don't know/unsure
Financial	How would you describe your financial situation?	1, Find it a strain to get by from week to week 2, Have to be careful with money 3, Able to manage without much difficulty 4, Quite comfortably off

		5, Very comfortably off 6, Prefer not to answer
Exercise_use	Do you currently participate in regular exercise and/or physical activity (e.g. strengthening program, Pilates, walking, cycling etc)	1, No 2, Yes, 1 time per week 3, Yes, 2-3 times per week 4, Yes, 4-5 times per week 5, Yes, 6+ times per week
Careseeking	Have you ever sought formal treatment for knee pain at any time in your life (e.g. treatment from a doctor, physiotherapist, chiropractor, surgeon, or any other healthcare provider)?	1, Yes 2, No
Knee_pain	Have you experienced activity-related pain in either of your knee joints in the past three months?	1, Yes 2, No
Joint	In which knee joint(s) have you experienced pain in the past 3 months?  [only for those who self-report knee pain in past 3 months]	1, Left knee only 2, Right knee only 3, Both knees
Knee_treatment	Have you sought formal treatment for your knee pain in the past 3 months (e.g. treatment from a doctor, physiotherapist, chiropractor, surgeon, or any other healthcare provider)?  [only for those who self-report knee pain in past 3 months]	1, Yes 2, No
Pain	Select the number which indicates the average amount of pain felt over the PAST WEEK in your most painful knee.  [only for those who self-report knee pain in past 3 months]	NRS ranging from 0 ('no pain') to 10 ('worst pain possible')
Function	Select the number which indicates how much your most painful knee has interfered with your physical function over the PAST WEEK.  [only for those who self-report knee pain in past 3 months]	NRS ranging from 0 ('no interference') to 10 ('maximal interference with function')
Surgery_use	Have you ever had knee surgery in the past?	1, Yes 2, No
Medication_use	Do you regularly take medication for pain relief for a musculoskeletal condition?	1, Yes 2, No
Health_literacy	How easily can you read and understand written health information? I find it...	5-point Likert scale with response options: 1, Always difficult 2, Difficult 3, Neither easy nor difficult 4, Easy 5, Always easy

Domain	Question	Scale
Primary outcome measures		
X-ray_diag	
Baseline: If you were told by your doctor that you had knee osteoarthritis, would you think an x-ray is necessary to confirm the diagnosis?
 
Post-intervention: Having read the information sheet, if you were told by your doctor that you had knee osteoarthritis, would you think an x-ray is necessary to confirm the diagnosis?
	11-point Numeric Rating Scale (NRS) ranging from 0=definitely unnecessary to 10=definitely necessary
Surgery	
Baseline: If you were told by your doctor that you had knee osteoarthritis, would you think joint replacement surgery (to replace the affected joint with an artificial joint) is necessary for your knee at some stage?
 
Post-intervention: Having read the information sheet, if you were told by your doctor that you had knee osteoarthritis, would you think joint replacement surgery (to replace the affected joint with an artificial joint) is necessary for your knee at some stage?
	11-point NRS ranging from 0=definitely unnecessary to 10=definitely necessary
Secondary outcome measures		
Beliefs about treatment options		
Exercise	
Baseline: If you were told by your doctor that you had knee osteoarthritis, would you think exercise and physical activity is helpful to manage it?
 
Post-intervention: Having read the information sheet, if you were told by your doctor that you had knee osteoarthritis, would you think exercise and physical activity is helpful to manage it?
	11-point NRS ranging from 0=definitely not helpful to 10=definitely helpful
Exercise_damage	
Baseline: If you were told by your doctor that you had knee osteoarthritis, would you think exercise and physical activity would damage your knee?
 
Post-intervention: Having read the information sheet, if you were told by your doctor that you had knee osteoarthritis, would you think exercise and physical activity would damage your knee?
	11-point NRS ranging from 0=definitely would not damage it to 10=definitely would damage it

Domain	Question	Scale
Medication	
Baseline:  If you were told by your doctor that you had knee osteoarthritis, would you think medication is helpful to manage your knee symptoms?
 
Post-intervention:  Having read the information sheet, if you were told by your doctor that you had knee osteoarthritis, would you think medication is helpful to manage your knee symptoms?
	11-point NRS ranging from 0=definitely not helpful to 10=definitely helpful
Xray_determine	
Baseline:  If you were told by your doctor that you had knee osteoarthritis, would you think an x-ray is necessary to determine the best treatment for your knee?
 
Post-intervention:  Having read the information sheet, if you were told by your doctor that you had knee osteoarthritis, would you think an x-ray is necessary to determine the best treatment for your knee?
	11-point NRS ranging from 0=definitely unnecessary to 10=definitely necessary
OA Knowledge		
Knowledge	
An 11-item questionnaire with the following questions:
 
 
1. Your knee joint wears out with everyday use
 
2. Osteoarthritis will only get worse over time
 
3. Increased knee pain always means that you have damaged your knee
 
4. You need an x-ray or scan to know if you have osteoarthritis
 
5. Being active makes osteoarthritis feel better
 
6. Keeping a healthy body weight is a key part of osteoarthritis care
 
7. X-rays or scans show how much your osteoarthritis affects you
 
8. Making your leg muscles stronger improves your ability to do daily tasks
 
9. Pain from osteoarthritis can be managed without surgery
 
10. Exercises can ease pain as much as most medications
 
11. Most people with knee osteoarthritis will need a joint replacement at some point
 
	
Each statement rated as False (1), Possibly False (2), Unsure (3), Possibly True (4), or True (5). Each item is scored on a scale from 1 to 5. Items 1,2, 3, 4, 7, and 11 are reverse scored and added to items 5, 6, 8, 9, and 10. Scores range from 11-55 with higher scores indicating greater/more accurate knowledge about osteoarthritis.

Level of concern		
Concern	
Baseline:  If you were told by your doctor that you have knee osteoarthritis, how concerned would you be that your knee problem would get worse in the future?
	
4-point Likert scale with response options:  1, Not at all concerned  2, A little concerned  3, Quite concerned

Domain	Question	Scale
	Post-intervention: Having read the information sheet, if you were told by your doctor that you have knee osteoarthritis, how concerned would you be that your knee problem would get worse in the future?	4, Very concerned
Process measures		
Satisfaction		
Satisfaction_post	If you were told by your doctor that you had knee osteoarthritis, how satisfied would you be with the information provided to you in the information sheet that you just read?	1, Very dissatisfied 2, Dissatisfied 3, Neutral 4, Satisfied 5, Very satisfied
Time spent reading information pamphlet		
Qualtrics_timeonpage	Measured by Qualtrics	Minutes
Selfreportedtimeonpage	Self-reported	Minutes (open text box)

## Appendix 2

